5.3 LIFESTYLE CONSIDERATIONS

Participants will be informed that the risk of complications from metformin, particularly lactic acidosis, can increase with excessive alcohol intake. In addition, study medication should be stopped in other acute conditions that could lead to lactic acidosis, including diarrhea and vomiting, acute renal failure, and hospitalizations for acute infection that could lead to sepsis or involve sepsis. IP may be resumed when these situations have resolved.

5.4 SCREEN FAILURES

Screen failures will be excluded from the study.

5.5 STRATEGIES FOR RECRUITMENT AND RETENTION

To ensure the trial accrues and retains the number and diversity of participants required to assess the primary and secondary endpoints, a recruitment and retention risk and needs assessment to identify areas of concern and opportunities for engagement will be conducted. Our approach will recognize and support the diverse needs of study sites (clinicians, research staff, and informatics staff), meaningfully involve participants, families, community groups and clinicians in all stages of the study. Site-specific recruitment planning will be done with guidance from the master recruitment and retention plan allowing adaptation to the sites' local IRB requirements and institutional marketing practices. We will use an ongoing evaluation process, which will include iterative feedback from the recruitment reports, sites, and study participants and will guide implementation activities and adapt as needed. A portfolio of recruitment materials such as flyers, posters, phone and email scripts, and social media ads will be available to be personalized for local sites. All recruitment materials and scripts will be approved by the IRB prior to use. These assets will be available electronically. Each participating site will be able to choose recruitment and retention strategies that fit their local setting such as:

- Broad targeted advertisements (e.g., brochures/flyers, web advertisements and notices, social network advertisements including but not limited to Facebook, Twitter and Instagram, and media advertisements on television, radio and newspapers).
- Direct-to-participant (e.g., mail, health system portals, calls, waiting rooms, or clinical team)
- Social and community networks (e.g., social media, support group newsletters or community events)

Potential strategies to be employed regarding screening and recruitment include:

Pre-Screen/Screening

- Phone calls will be made to potential participants identified through EHR, registries, and those who respond to ads.
- Unsolicited “cold calls” to potential participants will only be made at sites where this practice is approved by the local IRB. If approved, the study coordinator will use the *Telephone Screening Script* to discuss the study with the potential participant.
- If unsolicited “cold calls” are not permitted by the local IRB, such calls will not be conducted.
- An alternative to the unsolicited “cold call” is the use of MyChart (an Epic EHR product) or similar EHR-based communication tool. Use of EHR based communication will only be conducted based on local site practices and with local IRB approval. The communication text is outlined in the document, *EHR-based Recruitment Communication*.

- Potential participants will be encouraged to share study information and study contact phone number or website with friends/family who may interested in participating in the study
- Potential participants will be asked for recommendations on possible recruitment sites.
- Potential participants will be invited to register on Alzheimer's registries, general research recruitment registries including but not limited to ResearchMatch
- Potential participants will be asked, "How did you hear about the study?"
- Additional centralized pre-screening may occur through recruitment websites using a dedicated call-in center at Columbia University.

Consenting

- Potential participants will be given opportunities to ask questions about study
- Recruitment and retention team members will begin building rapport with participants
- Medical care providers will be informed of participant enrollment (when possible, or as required) and provided with study brochure or one-page flyer.

Potential strategies to promote engagement and retention of participant could include:

- Return of laboratory results
- Phone calls
- Reminder cards
- Holiday Birthday cards
- All participants and study partners will be offered a perk for participation, such as an Amazon Prime membership for the duration of the study or a gift card of similar value.

The DCC and CCMC will compile reports to generate a master log of participant attrition and missed visits. This log will be monitored to guide and inform continuous process improvement.

6 STUDY INTERVENTION

6.1 STUDY INTERVENTION(S) ADMINISTRATION

6.1.1 STUDY INTERVENTION DESCRIPTION

There will be 2 study arms, extended-release metformin (Glucophage XR® 500 mg tablets [reduced mass]; 2,000 mg a day maximum dose), and matching placebo with identical appearance. IP will be supplied by EMD Serono Research & Development Institute and delivered in bulk to the research pharmacy at the University of Iowa, which will prepare bottles with IP. These will be sent to the University of Rochester, which will prepare kits of IP for dispensation. The University of Rochester will send these kits to the local pharmacies of participating clinical sites for dispensation.

6.1.2 DOSING AND ADMINISTRATION

IP will be titrated every 10 days by one tablet (500 mg), up to 2000 mg a day. Participants will remain in the study on the maximum tolerated dose and will be considered in the analyses on an intent to treat basis.

6.2 PREPARATION/HANDLING/STORAGE/ACCOUNTABILITY

6.2.1 ACQUISITION AND ACCOUNTABILITY

The central research pharmacy for the study will be located at the Clinical Materials Services Unit (CMSU) at the University of Rochester. The University of Iowa Pharmaceuticals (UIP) will receive Glucophage XR® 500 mg tablets [reduced mass] and matching placebo in bulk (drums of 24,828 tablets for metformin, drums of 13,800 for placebo) from the EMD Serono Research & Development Institute, who will supply the IP. The UIP will prepare bottles of IP with a 140 count (35-day supply at maximum dose). The CMSU will receive approximately 4,900 x 140-count bottles each of metformin 500 mg tablets and matching placebo tablets from the UIP divided over three shipments. These quantities of study drug will support 326 participants, randomized 1:1 (active:placebo) and includes an overage factor of 40% for baseline kits and 10% for resupply kits. Upon receipt of the investigational products, the CMSU will perform a visual inspection and quality assurance (QA) release of all incoming materials to confirm that the appropriate quantities were received in good condition. Using the randomization code provided by the DCC), the CMSU will generate the necessary bottle and kit box labels that will support the double-blind, 1:1 (active:placebo) design of the study.

6.2.2 FORMULATION, APPEARANCE, PACKAGING, AND LABELING

The CMSU will label the study drug and configure the 140-count bottles into six-month kits delivered to the site local research pharmacy containing two three-month kits with 3 bottles each. The study site local research pharmacy will dispense the study drug to participants by mail or will dispense the study drug to the CRC who will provide it to the participant at the in-person study visit or by mail. Study drug may be dispensed as two 3-month kits every six months or one kit every 3 months, whichever is preferred by the participant. The CMSU will generate the necessary bottle and kit box labels that will support the double-blind, 1:1 (active:placebo) design of the study.

Sites will maintain accurate records of study kits in the EDC inventory form. When inventory falls below par (periodic automatic replenishment) level, study kits will be replenished by CMSU.

6.2.3 PRODUCT STORAGE AND STABILITY

IP tablets are to be kept in the container in which they are supplied and are to be kept tightly closed. To protect young children from poisoning, we advise that safety caps be kept locked, and the medication be immediately placed in a safe location out of sight and reach of children. Tablets should be stored in the medication bottle at room temperature and away from light, excess heat, and moisture (not in the bathroom). Any unused tablets are to be returned to study personnel.

6.2.4 PREPARATION

For this study, the IP tablets will be prepared by the study pharmacy. No preparation is required by study staff or study participants. The IP will be administered as an extended-release tablet taken by mouth, taken once daily with the evening meal. Participants will be instructed to follow the directions on the prescription label carefully and ask the doctor or study pharmacist to explain any part not understood. Participants will be instructed to take the IP exactly as directed and to not take more or less of it as prescribed by the healthcare provider. The IP tablets are to be swallowed whole. They are not to be split, chewed, or crushed.

6.3 MEASURES TO MINIMIZE BIAS: RANDOMIZATION AND BLINDING

Randomization: eligible participants will be randomized in 1:1 ratio to receive either metformin or placebo, using randomly permuted block randomization stratified by each site to achieve balance of treatment assignment overall and by site.

Blinding: participants, providers, outcome assessors and biostatisticians will be blinded to the treatment assignment. One group of biostatisticians will be unblinded to the treatment assignment to provide reports to the MAP data and safety monitoring board (DSMB).

6.4 STUDY INTERVENTION COMPLIANCE

Compliance with the study intervention will be monitored by direct discussion at monthly telephone calls and face-to-face study visits (every six months).

6.5 CONCOMITANT THERAPY

For this protocol, a prescription medication is defined as a medication that can be prescribed only by a properly authorized/licensed clinician. Medications to be reported in the CRF are concomitant prescription medications (up to two months prior to baseline), over-the-counter medications and supplements.

All concomitant prescription medications will be recorded in the CRF at screening and at each study visit as outlined in Table 7. Study Assessments and Procedures.

6.5.1 RESCUE MEDICINE

Not applicable

7 DISCONTINUATION OF STUDY INTERVENTION AND WITHDRAWAL OF PARTICIPANT

7.1 DISCONTINUATION OF STUDY INTERVENTION

Discontinuation of IP does not mean discontinuation from the study, and remaining study procedures should be completed as indicated by the study protocol. If a clinically significant finding is identified (including, but not limited to changes from baseline) after enrollment, the investigator or qualified designee will determine if any change in participant management is needed. Any new clinically relevant finding will be reported.

If participants develop diabetes by HbA1c criteria (6.5% or higher), they will be referred to their physicians to decide about treatment for diabetes. This may lead to discontinuation of IP upon consultation with the study's safety officer at the DCC. However, participants will be invited to remain in the study and will be analyzed following intent to treat.

If the medication is not discontinued due to an SAE and the investigator believes that the participant could be re-challenged with the discontinued medication per standard clinical practice, then this may be attempted after discussion with the DSMB and approval by the Medical Monitor.

If the medication was discontinued due to an SAE, then there should not be an attempt to restart the medication.

Any discontinuation of study drug will be recorded on the Dose Change Log eCRF.

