Fever	Consultation with PMD the same day
Vomiting/diarrhea	If unable to hydrate by mouth, refer to emergency room/call 911; otherwise, advise consultation with PMD the same day. Withhold study medication until vomiting and diarrhea have stopped, and dehydration has resolved.
Headache	If clearly migraine or tensional headache, advise to take prescribed medications; if no improvement, consult with PMD same day. If no changes in mental status or neurologic deficits, if blood pressure <160, consultation with PMD same day; otherwise, refer to emergency room/call 911
Weight loss/no medical follow-up	Consult with PMD the same day If no PMD, see contacts below
Acute renal insufficiency (azotemia), for any reason, including post-renal (e.g., obstruction), pre-renal (e.g., dehydration), or intrinsic (e.g., acute tubular necrosis)	Stop IP until the cause of acute renal insufficiency has resolved and renal function has improved to at least a GFR of 45 mL/min or higher
Any other condition treated	Advise consultation with MD. Provide contact numbers (see below)
IF IN DOUBT	Contact PI or study physician

Table 6. Medical Contingencies: Summary of Conditions and Actions

Vulnerable participants

No vulnerable populations will be included in this study.

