8.3.2 DEFINITION OF SERIOUS ADVERSE EVENTS (SAE)

An AE is considered "serious" if, in the view of either the investigator or sponsor, it results in any of the following outcomes:

- Death
- A life-threatening adverse event that places the participant at immediate risk of death at the time of the event as it occurred.
- Inpatient hospitalization or prolongation of existing hospitalization
- A persistent or significant incapacity or substantial disruption of the ability to conduct normal life functions, or a congenital anomaly/birth defect.
- Important medical events that may not result in death, be life-threatening, or require hospitalization may be considered serious when, based upon appropriate medical judgment, they may jeopardize the participant and may require medical or surgical intervention to prevent one of the outcomes listed in this definition. This determination is based on the opinion of either the investigator or sponsor.

The following hospitalizations are not considered SAEs:

- Visits to the emergency room or other hospital department lasting less than 24 hours that do not result in admission (unless considered an "important medical event" or a life-threatening event);
- Elective surgery planned before or after signing consent;
- Medical/surgical admissions other than remedying ill health state that were planned before study entry. Appropriate documentation is required in these cases;
- Admissions encountered for another life circumstance that have no bearing on health status and require no medical/surgical intervention (e.g., lack of housing, economic inadequacy, caregiver respite, family circumstances, administrative reason).

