8.3.5 ADVERSE EVENT REPORTING

The site investigator is responsible for monitoring the safety of participants enrolled into the study. If an adverse event necessitates modification of study drug dosing, this will be captured on the Dose Change Log eCRF.

All AEs and SAEs occurring from the first day of study enrollment (the day of randomization) to 30 days post last day of study drug dosing will be captured in the AE and SAE eCRF. Unless exempted as described in section 8.3.2, all SAEs, whether or not deemed drug-related or expected, must be reported to the CCC by the investigator or qualified designee **within 24 hours** of first becoming aware of the event. The investigator or qualified designee will enter the required information regarding the SAE into the appropriate module of the eCRF, which will automatically result in distribution of the information to the site-monitoring group, the Safety Event Adjudication Committee, and EMD Serono.

Pregnancy and cancer are not always serious by regulatory definition; however, these events must be submitted to the sponsor within the same time period as an SAE via the EDC.

If the eCRF system is temporarily unavailable, the event, including the investigator-determined causality to study drug should be reported via the back-up paper SAE form to Safety Surveillance. Upon return of the availability of the electronic data capture (EDC) system, the SAE information must be entered onto the eCRF.

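### Section 7.1 bars restarting study drug discontinued due to an SAE, but 5.3 allows resumption after a hospitalization for acute infection or sepsis, which is an SAE

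*Protocol*

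**What the plan says.** Section 7.1 gives two rules for drug that has been discontinued. If the reason was not an SAE, re-challenge may be attempted after discussion with the DSMB and approval by the Medical Monitor. If the reason was an SAE: "If the medication was discontinued due to an SAE, then there should not be an attempt to restart the medication". The second rule has no exception, is not limited to drug-related events, and does not refer to any other section.

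Section 5.3 says that "study medication should be stopped in other acute conditions that could lead to lactic acidosis, including diarrhea and vomiting, acute renal failure", and adds to that list "hospitalizations for acute infection that could lead to sepsis or involve sepsis. IP may be resumed when these situations have resolved".

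Table 6 in section 2.3.1 has a row for acute renal insufficiency: "Stop IP until the cause of acute renal insufficiency has resolved and renal function has improved to at least a GFR of 45 mL/min".

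Section 8.3.2 lists among the SAE criteria "Inpatient hospitalization or prolongation of existing hospitalization". Its exemptions are short visits ("Visits to the emergency room or other hospital department lasting less than 24 hours that do not result in admission"), elective surgery, admissions planned before study entry for reasons other than ill health, and admissions for social or administrative reasons.

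**The concern.** Section 5.3 names these conditions because they can lead to lactic acidosis, which section 2.2.2 calls the most serious side effect of metformin. Whether drug goes back on afterwards is a safety and dosing instruction, so it should have one answer. Both sets of rules stop drug during the event. They differ on what happens once it resolves: 5.3 and Table 6 treat the stop as temporary, while 7.1, read literally, makes it permanent if the event was an SAE.

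At stake is consistent handling across sites. A site that resumes drug under 5.3 can be cited under 7.1, since section 10.1.10 counts any noncompliance with the protocol as a deviation. A site that applies 7.1 ends treatment that 5.3 regards as paused. A statistical analysis plan would not settle this, because it is an instruction to sites about dosing.

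**Working it through.** No arithmetic applies. The check sets the rules side by side.

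**Step 1: does each 5.3 condition meet the 7.1 bar?**

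| Condition in 5.3 | Rule for resuming | SAE under 8.3.2? | Restart under 7.1 |
|---|---|---|---|
| Hospitalization for acute infection that may lead to or involve sepsis | 5.3: may resume once resolved | Yes: an inpatient admission, and no exemption fits | Barred |
| Acute renal failure or insufficiency | 5.3: may resume once resolved. Table 6: stop until the cause has resolved and GFR is at least 45 mL/min | Only if the event meets an SAE criterion | Barred only then |
| Diarrhea and vomiting | 5.3: may resume once resolved. Table 6: withhold until settled and dehydration has resolved | Not by its own wording; an emergency visit under 24 hours without admission is normally exempt | Not part of this point |

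The first row conflicts by its own wording: the event that triggers the 5.3 stop is itself a hospitalization. The second row conflicts conditionally.

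**Step 2: does the protocol separate a hold from a discontinuation?** Some wording points that way:
- Table 6 uses stop-until and withhold-until phrasing.
- Section 8.3.8 lists hospitalizations among events that require holding metformin.
- Section 8.3.9 adds *permanently* to *discontinued* for pregnancy.

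Other wording points against it:
- Section 2.3.1 uses *discontinued* for a stop on the day before surgery or contrast that may end 48 hours after the procedure.
- Section 7.1 itself speaks of re-challenge with drug it calls *discontinued*, so within that section the word does not mean permanent.

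No section defines either term.

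**Step 3: does the recording system show which rule applies?** Section 7.1 says "Any discontinuation of study drug will be recorded on the Dose Change Log eCRF", and section 8.3.5 says "If an adverse event necessitates modification of study drug dosing, this will be captured on the Dose Change Log eCRF". Both kinds of stop go to the same log, and the protocol does not say how an entry is classed as a hold or a discontinuation.

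**Step 4: does another section decide?** Section 2.3.1 has the medical monitor consulted on stoppage for suspected side effects or contraindications. Nothing says whether 5.3 and Table 6, or 7.1, governs restart after one of these stops when the event is an SAE.

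**The case against.** The strongest reply is that 7.1 was never meant to cover precautionary stops. If it governed every stop, each diarrhea hold and each peri-procedural pause would need DSMB discussion and Medical Monitor approval before drug went back on, and the sections that describe those pauses ask for neither. Most of the vocabulary fits a split between holding and discontinuing, and the specific rules in 5.3 and Table 6 would ordinarily prevail over the general rule in 7.1. This is a plausible account of the intent. It does not remove the problem, because the protocol never states it and the wording of 2.3.1 and 7.1 undercuts it.

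Three further points on that side stand:
- A reader might infer that sites are forced into a breach whatever they do. They are not. Section 5.3 is permissive and Table 6 says when a stop may end, so a site that leaves drug off breaches neither. The compliant path exists and is the more cautious one.
- A reader might infer that every acute condition in 5.3 conflicts with 7.1. Only the infection hospitalization does so by its own wording; the renal case depends on seriousness.
- The Data Safety Monitoring Plan (cited in 8.3.8) and the Manual of Procedures (cited in 10.1.10) are not available here and may instruct sites more clearly. It cannot be said that sites do diverge, only that the protocol text allows it.

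**Conclusion.** The conflict is real but narrow. For a hospitalization for acute infection or sepsis, 7.1 bars the restart that 5.3 permits. For acute renal failure or insufficiency, the same is true when the event meets an SAE criterion. This assumes that *hospitalizations* in 5.3 means inpatient admission and that a stop under 5.3 or Table 6 counts as a discontinuation due to the event. The protocol neither states nor rules out the second assumption, and that is the defect.

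The size cannot be quantified, because the protocol gives no rate for these events and so no count of participants or lost drug time can be derived. It would be wrong to infer harm to the primary analysis. Participants who stop drug remain in the study and are analyzed by intent to treat, dose changes and their reasons are recorded, and the ITT set, alpha and sample size do not move. It is worth fixing because the instruction concerns safety and the correction is cheap.

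**What to change.** Make three changes:
- Add to 7.1 that precautionary temporary interruptions under 2.3.1, 5.3, Table 6 and 8.3.8, including those during an SAE hospitalization, are holds rather than discontinuations. They may be resumed under those sections' own criteria once the event has resolved.
- Limit the no-restart rule in 7.1 to SAEs suspected to be related to study drug or leading to a decision to discontinue definitively.
- In the surgery and contrast sentence of 2.3.1, change *discontinued* to *held*.

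The first change should name all four places. Exempting only 5.3 and Table 6 would leave an unplanned surgical admission (2.3.1) and other hospitalization holds (8.3.8) under the no-restart rule.

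If the sponsor does intend the strict rule, add *unless the event is an SAE* to the resumption wording in 5.3 and in the Table 6 renal row.

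The cost is a short amendment and a memo to sites. No new visits, participants or data collection are needed, since dosing changes and their reasons are already captured under 8.3.5 and 8.3.8.
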